11.3. Subject Information

For all subjects, demographic characteristics (eg, age, height, weight, body mass index [BMI], race, and gender), and other baseline characteristics (eg, physical examination, medical history, concomitant diseases) will be tabulated and summarized with descriptive statistics.

11.4. Immunogenicity Analyses

No formal hypothesis on immunogenicity will be tested. The analysis of immunogenicity will be done on the immunogenicity and per-protocol populations as defined in Section 11.1.

Descriptive statistics (actual values and changes from reference) will be calculated for continuous immunologic parameters at all time points. Graphical representations of changes in immunologic parameters will be made as applicable. Differences between groups at a specific time point will be tested for exploratory purposes by a 2-sample t-test if the data appear to be normally distributed. If not, the non-parametric Wilcoxon rank sum test will be used. If portions of the measurements are censored below the assay quantification limit, the Gehan-Wilcoxon test will be employed. All statistical tests will be two-sided and will be considered statistically significant if $p<0.05$.

Frequency tabulations will be calculated for discrete (qualitative) immunologic parameters at all time points. Significant differences between groups will be determined by a 2-sided Fisher's exact test.

Magnitude and breadth of (neutralizing) antibody responses will be explored graphically through the generation of individual magnitude-breadth (M-B) curves. The area under the M-B curve (AUC) provides an overall summary of the M-B profile. The AUCs will be compared between groups using the Wilcoxon-Mann-Whitney test.

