5. VACCINE ALLOCATION AND BLINDING

Study Vaccine Allocation

Procedures for Randomization

Central randomization will be implemented in this study. Subjects will be randomly assigned to one of eight treatment groups based on a computer-generated randomization schedule prepared before the study by or under the supervision of the sponsor. The randomization will be balanced by using randomly permuted blocks and stratified by region (US, Africa, and Asia). Efforts will be made to enroll a minimum of 50 subjects from each region.

The interactive web response system (IWRS) will assign a unique treatment code, which will dictate the treatment assignment and matching study vaccine for the subject. The requestor must use his or her own user identification and personal identification number when contacting the IWRS, and will then give the relevant subject details to uniquely identify the subject.

Blinding

The subjects, clinical staff, and investigator, will be blinded to study vaccine allocation until Week 96. The sponsor will be blinded to study vaccine allocation until the Week 28 analysis (see Section 11.6). The pharmacist with primary responsibility for vaccine dispensing will not be blinded to the study vaccine.

A pharmacist will prepare study vaccine for administration and will provide it to the clinic. In order to preserve blinding, he/she will place an overlay on the syringes. Administration of study vaccine to the subjects can be performed by a qualified healthcare provider from the study site (including the pharmacist who prepared the study vaccine) who will have, on the day of administration, no other study function related to safety, study data evaluation or recording of AEs for those subjects that he/she vaccinated on that day. More information and details on the preparation of vaccine and adjuvant components, as well as details on the holding time and storage conditions from the time of preparation to delivery of the study vaccine, are provided in Section 14.

The investigator will not be provided with randomization codes. The codes will be maintained within the interactive web response system (IWRS), which has the functionality to allow the investigator to break the blind for an individual subject.

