In addition to an HIV-risk assessment, counseling related to avoidance of HIV infection, pre- and post-HIV test counseling, and pregnancy counseling will be provided to all subjects (men and women).

Visit 6: Week 12/Vaccination 2

An abbreviated physical examination (including weight measurement), measurement of vital signs, and cardiac risk assessment will be performed for all subjects pre-vaccination. A pre-dose blood sample for humoral immunogenicity assessment will be drawn, and for assessment of Ad26 seropositivity. A urine pregnancy test must be performed before vaccination for women of childbearing potential, and results must be available and negative prior to vaccination. Pre-dose samples for hematology, biochemistry, urinalysis, and HIV testing will be collected.

After vaccination, subjects will remain under observation for at least 30 minutes for reactogenicity, and vital signs measurement will be repeated.

All AEs will be recorded on the CRFs, together with information about any concomitant medications.

Subjects will be provided a memory aid, thermometer, and ruler to measure and record local solicited AEs and body temperature. Subjects will also note symptoms of unsolicited and solicited systemic AEs through the memory aid for 8 days post-vaccination (day of vaccination and the subsequent 7 days).

In addition to an HIV-risk assessment, counseling related to avoidance of HIV infection, pre- and post-HIV test counseling, and pregnancy counseling will be provided to all subjects (men and women).

Visit 9: Week 24/Vaccination 3

The procedures for Week 24 will be the same as at Visit 6 as detailed above. Additionally at Week 24, subjects will complete a Social Impact Questionnaire ([Attachment 4](#)).

Visit 13: Week 48/(Booster) Vaccination 4

The procedures for Week 48 will be the same as at Visit 6 as detailed above. Additionally, at Week 48, subjects will complete a Social Impact Questionnaire ([Attachment 4](#)).

9.1.5. Post-vaccination Follow-Up Phase (Weeks 1, 2 and 4; Weeks 14 and 16; Weeks 26, 28 and 36; Weeks 50 and 52)

Visits 2a, 3, 4, and 5 (Days 2-4, and Weeks 1, 2, and 4)

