9.2. Immunogenicity

9.2.1. Endpoints

The primary immunogenicity endpoints will be defined as the Env-C ELISA binding antibody titer and breadth of Env-binding antibody response across Clades A, B, and C measured at Week 28.

For evaluation of humoral responses:

- Env-specific binding antibody titers (ELISA) 4 weeks after the third and fourth vaccinations, covering Clades A, B, and C.
- HIV nAb titers for Tier 1 and Tier 2 viruses covering Clades A, B, and C; note: Tier 2 will be assessed only if Tier 1 shows positive results.
- Functional antibodies as assessed by antibody-dependent cellular phagocytosis (ADCP) assay.

For evaluation of T-cell responses:

- Assays of peptide pool sets covering the Gag, Env or Pol will be evaluated by standard ELISPOT criteria ¹⁷ with additional mapping of positive pools to determine the number of positive epitopes for each individual, at baseline and at 2 and 4 weeks after the third and fourth vaccinations.

For durability of responses:

- Immunogenicity assays at 12, 30, and 48 weeks after the last vaccination. Durability of responses to be followed approximately 5 years after Week 96 in selected group(s) (see Section 9.1.8).

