11.2. Sample Size Determination

A sample size of 50 subjects per regimen is regarded to be appropriate to assess the safety and tolerability of the different vaccine regimens and also collect sufficient data on immunogenicity. Placebo recipients are included for blinding and safety purposes and will provide control specimens for immunogenicity assays.

While mild to moderate vaccine reactions (local injection site and systemic responses) are expected, AEs that preclude further dose administration or more serious ones that would limit product development are not anticipated. With 50 individuals in a vaccine regimen, the observation of 0 such reactions would be associated with a 95% confidence that the true rate is less than 6%. For the combined groups with Ad26.Mos.HIV (n = 350), there would be 95% confidence that the true rate is <1% when 0 events are observed. The following table shows the probabilities of observing at least one AE at given true AE rates:

| True AE rate | Probability of observing at least one AE in n subjects | |
|--------------|--|---------|
| | n = 50 | n = 350 |
| 0.1% | 5% | 30% |
| 0.5% | 22% | 83% |
| 1% | 39% | 97% |
| 2.5% | 72% | 100% |
| 5% | 92% | 100% |
| 10% | 99% | 100% |

The primary population for the safety analyses will consist of all subjects who received at least one dose (Ad26.Mos.HIV or placebo).

The immunogenicity population will consist of all subjects who received at least one dose and have at least one measured post-dose blood sample collected. Anticipating a dropout rate of approximately 10%, 45 evaluable subjects per group will allow detection of 2.3-fold differences in Env-binding antibody titers, generally accepted to be biologically relevant, between groups with 80% probability, assuming a two-sided 5% Type I error and a standard deviation of 0.6 on the \log_{10} scale.

Groups will be combined to make comparisons between different viral vectors (groups combined over the different protein doses, N=135 per group) or between different protein doses (groups combined over different viral vectors, N=90 per group). Under the same assumptions as above, this will allow detection of 1.6-fold (N=135/group) to 1.8-fold differences (N=90/group) in Env-binding antibody titers. Potential statistical interactions will be explored by means of the appropriate interaction tests.

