## 6.5. Immune response assays: details

The details for each immune response assay are listed in following table. Final values of LLOQ/LOD might deviate from the table below, the dTA approved by the lab will be taken as source.

Assay	Test	Lab	Time Points	LLOQ	LOD	Unit	Responder definition (R)	Fold increase (FI) calculation
ELISA	AD26 VNA	Janssen Vaccines and Prevention	Wk0	17	NA	IC90	>LLOQ	NA
Env ELISA IgG-t gp140	Clade A (92UG037.1) Clade B (1990a) Clade C (Con C) Clade C (C97ZA.012)* Mos1	Janssen Vaccines and Prevention	Wk0 Wk 28 Wk 52 Wk78 Wk96	625 156.25 625 156.25 78.125	0	EU/ml	1) if baseline <LLOQ or missing, R>LLOQ 2) if baseline >=LLOQ, R=3-fold increase from baseline	1) if baseline >LLOQ, FI=Value post-baseline/Value wk0 2) if baseline<LLOQ, FI=value post-baseline/LLOQ
Env ELISA IgG1-4	Clade C (C97ZA.012) IgG1 Clade C (C97ZA.012) IgG2 Clade C (C97ZA.012) IgG3 Clade C (C97ZA.012) IgG4	BIDMC	Wk0 Wk 28 Wk 52 Wk78 Wk96	12.3 28.7 12.4 13.2	4	EC50		
Env ADCP gp140	Clade A (92UG037.1) Clade B (1990a) Clade C (Con C) Clade C (C97ZA.012)* Mos1	Ragon	Wk0 Wk 16 (n=72) Wk 28 Wk 52 Wk78 Wk96	NA	5.16 6.43 6.49 4.32 4.28	PS	1) if baseline <LOD, R>LOD 2) if baseline >=LOD, R=3-fold increase from baseline	1) if baseline >LOD, FI=Value post-baseline/Value wk0 2) if baseline<LOD, FI=value post-baseline/LOD
TZM-bl	Tier1 Clade C (MW965.26)	Duke U	Wk28 Wk52	20	NA	ID50	>LLOQ	NA
	Tier 2 Clade A (398F1) n Clade AC (246F3) n Ab Clade AE (CNE55) nAb Clade AE (CNE8) nAb Clade B (TRO11) nAb Clade B (X2278) nAb Clade BC (BBOX2000) nAb Clade BC (CH119) nAb		Wk28 (n=72)	10				

Assay	Test	Lab	Time Points	LLOQ	LOD	Unit	Responder definition (R)	Fold increase (FI) calculation
	Clade C ( Ce1176) nAb Clade C (25710) nAb Clade C (Ce0217 ) nAb Clade G (X1632) nAb							
BAMA IgG3	HIV ENV Con S gp140 CFI (Clade M) HIV ENV Con 6 gp120/B (Clade M) HIV ENV gp41 HIV ENV 1086C_D7gp120 (Clade C) HIV ENV 1086C gp140 (Clade C) HIV ENV 1086C_V1V2 (Clade C) HIV ENV gp70_B.CaseA_V1V2 (Clade B)	Duke U	Wk0 Wk 28 Wk 52 Wk78 Wk96	100 a	NA	MFI	BAMA interpretation= 1	1) if baseline >LLOQ, FI=Value post baseline/Value wk0 2) if baseline<LLOQ, FI=value post baseline/LLOQ
BAMA IgGA	Con S gp140 CFI Con 6 gp120/B gp41 1086C_D7gp120.avi/293F A1.con.env03 140 CF 00MSA 4076 gp140		Wk0 Wk 28 Wk 52 Wk78					
BAMA IgG1	Con S gp140 CFI Con 6 gp120/B gp41 1086C_D7gp120.avi/293F 1086C gp140C_avi C.1086C_V1_V2 Tags gp70_B.CaseA_V1_V2							

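### The between-regimen tests of Week 28 Env titre leave out region, the randomisation stratum, and the response to the shared prime; this costs precision, not validity

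*Protocol*

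**What the plan says.** Protocol Section 9.2.1 sets the primary immunogenicity endpoints as "Env-C ELISA binding antibody titer and breadth of Env-binding antibody response across Clades A, B, and C measured at Week 28". Comparing Env binding responses between regimens is a primary objective (Section 2.1).

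Table 4 gives Groups 1-7 the same Ad26.Mos.HIV dose at Weeks 0 and 12; they diverge only at Week 24. Group 8 receives placebo throughout. Section 5 describes allocation by "randomly permuted blocks and stratified by region (US, Africa, and Asia").

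On comparison, Section 11.4 says "Differences between groups at a specific time point will be tested for exploratory purposes by a 2-sample t-test" when the data look normal, with the Wilcoxon rank sum test otherwise and Gehan-Wilcoxon when values are censored. Section 11.2 compares breadth by Wilcoxon-Mann-Whitney. No covariate or stratum appears in any of these.

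Table 5 schedules Env ELISA at half a month and one month after vaccination 2 (Weeks 14 and 16). At Week 12, and by cross-reference Week 24, Section 9.1.4 says "A pre-dose blood sample for humoral immunogenicity assessment will be drawn". Week 24 is not, however, an Env ELISA timepoint in Table 5.

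SAP Section 6.3 gives group-wise geometric means, fold increases and responder rates with 95% CIs, and no between-group test. Fold increase is taken against Week 0: "1) if baseline >LLOQ, FI=Value post-baseline/Value wk0". SAP 6.5 lists Env ELISA at Weeks 0, 28, 52, 78 and 96; a footnote adds intermediate timepoints for Group 1 only. SAP 2.4 makes region an immunogenicity subgroup, with four categories.

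**The concern.** A trial that stratifies its randomisation would normally carry the stratum into the comparison. Stratification balances region across groups. If region affects titre, the unadjusted test still counts between-region variation as error, so its standard error is too large for the design and the test is conservative.

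The shared prime offers a second gain. Weeks 0-24 are a common run-in for Groups 1-7. A titre taken after vaccination 2 and before Week 24 cannot depend on which of those groups a subject is in, so it is a legitimate covariate. It may also predict the Week 28 titre better than the Week 0 value, which precedes any vaccine response.

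At stake is the sharpness of the regimen comparison on a primary endpoint that informed selection for later studies.

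**Working it through.** **Inputs.** From Protocol Section 11.2: "45 evaluable subjects per group will allow detection of 2.3-fold differences in Env-binding antibody titers", with 80% probability, "assuming a two-sided 5% Type I error and a standard deviation of 0.6 on the" log10 scale; pooled comparisons of 90 and 135 per group. Not in the documents, so assumed: the share of titre variance explained by region (0-20%), and the correlation r between post-prime and Week 28 log10 titre (0.3-0.7).

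**1. The protocol's own figures.** Detectable log10 difference = SD × √(2/n) × (1.960 + 0.842).
- n = 45: 0.6 × 0.2108 × 2.802 = 0.354, or 2.26-fold (2.28 by the noncentral t).
- n = 90: 0.6 × 0.1491 × 2.802 = 0.251, or 1.78-fold (1.79).
- n = 135: 0.6 × 0.1217 × 2.802 = 0.205, or 1.60-fold (1.60).

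The stated 2.3, 1.8 and 1.6 reproduce for the unadjusted two-sample comparison. Power for 2.3-fold (0.3617 log10) at n = 45 is 81.6%, or 80.7% by the noncentral t.

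**2. Region.** Let region explain a share R of total variance and be balanced across groups. The difference in means then has true SE 0.6 × √(1−R) × √(2/n), while the t-test uses about 0.6 × √(2/n). The effective critical value becomes 1.960/√(1−R).
- R = 0: 1.960, error rate 5.0%; adjustment changes nothing.
- R = 0.10: 1.960/0.949 = 2.066, error rate 3.9%.
- R = 0.20: 1.960/0.894 = 2.191, error rate 2.8%.

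Simulation of two groups of 45 over three equal regions agrees within simulation error (about 3.5-3.9% and 2.6-3.1%). A model with region restores about 5%.

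Power for 2.3-fold at n = 45:
- R = 0.10: SE = 0.569 × 0.2108 = 0.120; 0.3617/0.120 = 3.01. Unadjusted Φ(3.01 − 2.07) = 83%; adjusted Φ(3.01 − 1.96) = 85%.
- R = 0.20: SE = 0.537 × 0.2108 = 0.113; 0.3617/0.113 = 3.20. Unadjusted Φ(3.20 − 2.19) = 84%; adjusted Φ(3.20 − 1.96) = 89%.

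**3. Post-prime titre (Groups 1-7 only).** Residual SD = 0.6 × √(1−r²); detectable fold by the noncentral t.

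| r (assumed) | Residual SD | n = 45 | n = 90 | n = 135 | Power for 2.3-fold, n = 45 |
|---|---|---|---|---|---|
| 0 | 0.600 | 2.28 | 1.79 | 1.60 | 81% |
| 0.3 | 0.572 | 2.20 | 1.74 | 1.57 | 84% |
| 0.5 | 0.520 | 2.04 | 1.65 | 1.51 | 90% |
| 0.7 | 0.428 | 1.80 | 1.51 | 1.40 | 98% |

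The gain is slight at 0.3 and substantial only from about 0.5. It shrinks if many post-prime titres lie below the LLOQ, which SAP 6.5 puts at 78.125 to 625 EU/ml depending on the antigen.

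**The case against.** The strongest reply is that nothing here is an error. After randomisation the unadjusted test is unbiased, its power is stated correctly, and it errs on the conservative side. Section 11.4 calls the tests exploratory with no formal hypothesis. The Synopsis bases selection on several assessments (Env strength and breadth, functional and neutralising antibody, epitope mapping, T cells), not on a p-value rule. Groups 1 and 2 have already been chosen on the Week 28 results, and SAP Section 1 says the Week 96 analysis will not be rerun. All of this stands. It limits the point to efficiency, but it does not change what Section 11.4 specifies, and region adjustment is free.

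A reader might infer more than the documents support:
- *That chance differences in prime response pass for regimen effects.* At r = 0.5 such imbalance could shift a two-group ratio by up to 1.33-fold (1.96 × 0.5 × 0.6 × 0.2108 = 0.124 log10). The 5% error rate and the confidence interval already allow for it. Adjustment narrows the interval; it does not remove a bias.
- *That the sample size is wrong, or a different regimen would have been chosen.* The sample size reproduces, and nothing in the documents shows a changed choice.
- *That region is ignored.* It is a pre-specified immunogenicity subgroup in SAP 2.4. It is absent only from the comparison.
- *That the prime adjustment needs only a change of wording.* The SAP lists intermediate ELISA for Group 1 alone.

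**Conclusion.** The point holds as a matter of precision. Protocol 11.4 compares Week 28 Env titres without the stratum used to randomise and without the pre-divergence response that the design makes available. The comparison is valid as written, and the 2.3-, 1.8- and 1.6-fold figures are right for it.

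For region, the cost is an error rate of about 3.9% or 2.8% in place of 5%, and roughly 2 or 5 points of power, if region explains 10% or 20% of variance with equal-sized regions. With no region effect the cost is nil. For the prime, the detectable difference at 45 per group could fall from 2.28-fold to 2.20, 2.04 or 1.80 at correlations of 0.3, 0.5 or 0.7. The documents give neither the variance share nor the correlation. The region change is worth making; the prime covariate is optional.

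**What to change.** **Protocol 11.4.** Make the between-regimen comparison of log10 Week 28 Env titre a linear model with group and randomisation region (US, Africa, Asia). Report adjusted geometric mean ratios with 95% CIs. Where the text now calls for Wilcoxon or Gehan-Wilcoxon, use a region-stratified rank test or a censored regression that includes region. Keep the unadjusted test as a sensitivity analysis.

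**SAP.** Add the model to Section 6.3 as a new item, since no between-group comparison exists there to amend. State how the four SAP regions (East Africa, South Africa, Thailand, USA) map to the three strata. Label the analysis supplementary, because the Week 28 and Week 96 analyses are already done.

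**Optional.** For comparisons among Groups 1-7, add log10 Week 16 Env titre, which Table 5 schedules, with a rule for missing or censored values. Never use it against placebo: Group 8 had no prime, so there the covariate is itself affected by treatment.

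**Cost.** Region adjustment takes some wording and one model on data already held. The Week 16 covariate may require assaying stored sera from Groups 2-7 (6 × 50 = about 300 planned subjects) and lengthen SAP 6.5 by one ELISA timepoint. The linear model covers titre only; the 0-3 breadth score would need the stratified rank test if it is to be adjusted too.

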11.5. Safety Analyses

No formal statistical testing of safety data is planned. Safety data will be analyzed descriptively (including 95% confidence interval).

Baseline for all safety parameters will be defined as the last evaluation done before the first dose of study vaccine.

Adverse Events and Reactogenicity

The verbatim terms used in the CRF by investigators to report AEs will be coded using the Medical Dictionary for Regulatory Activities (MedDRA). All reported AEs (local and systemic, solicited and unsolicited) with onset during the treatment period (ie, treatment-emergent AEs, and AEs that have worsened since baseline) will be included in the analysis. For each AE, the number and percentage of subjects who experience at least one occurrence of the given event will be summarized by group, including exact 95% confidence intervals. Summaries, listings, datasets, or subject narratives may be provided, as appropriate, for those subjects who die, who discontinue vaccinations due to an AE, or who experience a severe AE or an SAE. The analysis for solicited AEs will be done on those subjects in the safety population for whom reactogenicity assessments are available in the database. The analysis of unsolicited AEs will be done based on the safety population.

Clinical Laboratory Tests

Laboratory data will be summarized by type of laboratory test. Descriptive statistics (actual values and changes from reference) will be calculated for each laboratory analyte at baseline and at each scheduled time point. Graphical presentation of changes in laboratory tests will be made as applicable. Baseline refers to the pre-dose value on Day 1. If this value is not available, the value at screening will be used as baseline value. Laboratory abnormalities will be determined according to a modified version of the DAIDS Table for Grading the Severity of Adult and Pediatric Adverse Events (DAIDS AE Grading Table), Version 1.0 dated December 2004 (Clarification, August 2009) included in [Attachment 1](#), and in accordance with the normal ranges of the clinical laboratory. Laboratory abnormalities will be tabulated per treatment group.

Electrocardiogram (ECG)

All statistical analyses of ECG variables will use the centralized ECG over-read data.

The effects on cardiovascular variables will be evaluated by means of descriptive statistics and frequency tabulations.

Vital Signs

Descriptive statistics of pulse rate and blood pressure (systolic and diastolic) values and changes from baseline will be summarized at each scheduled time point. The percentage of subjects with values beyond pre-specified limits will be summarized.

Physical Examination

Physical examination findings will not be tabulated separately. Clinically relevant findings will be reported as AE and will be tabulated and listed as AEs. BMI will be calculated using the recording of height at screening. Body weight and BMI results will be tabulated and summarized descriptively.

Social Impact Questionnaire

Data from the Social Impact Questionnaire will be summarized using descriptive statistics.

